### 3.6.3 *Withdrawal criteria*

Subjects or/and representatives can withdraw their consent at their own request without given reasons at all time during the trial. This should be without disadvantages for the subject. However the investigator should try to perform a final visit to get concluding findings of investigation.

Subjects may be withdrawn from the trial for the following reasons

- At their own request or at request of the legal representative.
- At the instigation of the sponsor. If, in the investigator's opinion, continuation of the trial would be detrimental to the subject's well-being.
- For women, if it becomes known that the subject is pregnant.
- Aggravation of disease with life threatening events
- Severe side effects (for example retinopathy, cardiomyopathy, ECG-modifications, liver value elevation)
- The subject/ patient is non-compliant or uncooperative
- The subject/ patient is not able to participate due to an Adverse Event
- The subject/ patient has to take any concomitant drugs interfering with the study medication
- The subject/ patient is no longer able to participate for other medical reasons (e.g., surgery, other diseases, or death)

The investigator decides about withdrawal of subjects from the clinical trial in case of occurrence of criteria mentioned above.

In all cases, the reason for withdrawal must be recorded in the CRF and in the subject's medical records. In case of withdrawal of a subject at his/her own request, as far as possible the reason should be asked for and documented. The subject must be followed up and as far as possible; all examinations scheduled for the final trial day should be performed and documented and all trial medication should be collected at site.

All on-going serious adverse events of withdrawn subjects have to be followed up see 7.3.

Withdrawn subjects will not be replaced.

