#### 4.1.10 Not permitted medication

Each previous and concomitant medication has to be documented in detail.

**Systemetic steroids:** pulsed glucocorticoids in the 4 weeks before entry into the study (day 1) and throughout the trail (V4 in START block and V6 in STOP block) are not allowed. A continous daily or alternate day oral dose of glucocorticoids is allowed and has to be stable in the 4 weeks before entry into the study (day 1) and throughout the trail.

Not permitted medication	Comedications very carefully to be considered (further explanation in the text)
Hepatotoxic medications, also caution with alcohol	Antiepileptics
Inhibitors of the monoaminooxidase	Digoxin
Arrhythmogenic medications	Cyclosporine
Amiodarone	Methotrexate
Moxifloxacin	Corticosteroids
Halofantrin	Aminoglycosides
Metronidazole	Agalsidase-beta
Phenylbutazon	Iaronidase
Probenecid	Neostigmine, Pyridostigmine
Indomethacin	Antacids
Penicillamin	Caolin
Pyrimethamine/Sulfadoxine	Cimetidine
Other medications that decrease the convulsive threshold	Praziquantel
Bupropion	Rabies vaccination with HDCV
Mefloquine	Insulin, antidiabetics
Other antimalarial	Ampicillin
	Azathioprin
	Other disease-modifying antirheumatic drugs

Due to an increased risk of ventricular arrhythmias the use of arrhythmogenic medication, as for example amiodarone or moxifloxacin, is not permitted during the trial. Halofantrin can prolong the QT interval with increased risk of arrhythmias and is therefore not permitted during the trial.

It is prohibited to use other hepatotoxic medication or inhibitors of the monoaminooxidase during the trial. Adolescent patients should be explained that no larger quantity of alcohol should be consumed during the treatment with HCQ.

The use of medication, that lowers the convulsive threshold, as for example mefloquine and bupropion, is not allowed during the trial, as there is an increased risk for seizures. The effect of antiepileptics can be reduced by hydroxychloroquine.

The use of digoxin and cyclosporine is not prohibited during the trial, but investigators must be aware that hydroxychloroquine may increase the plasma concentrations of digoxin and cyclosporine. So in this case a strict control of plasma-drug-level is necessary to avoid intoxication with digoxin or cyclosporine.

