#### 4.2 Rescue medication or emergency treatment

There exists no special rescue medication in this trial. Children with interstitial lung disease often are very sick. So far we do not know which patient will benefit from the use of hydroxychloroquine and which will not. It is possible, that some patients will deteriorate during the trial. As no evidence based standards for treating interstitial lung disease in children exist, it is in the responsibility of the treating physician to decide, what the further treatment will be.

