## 8 STATISTICS

Details of the statistical analysis of the data collected in this trial will be documented in a Statistical Analysis Plan (SAP) that will be generated by IZKS Mainz and finalized before closing the data base and prior to breaking the blind. The SAP is based on the protocol including all amendments. The document may modify the plans outlined in this protocol; however any major modifications of the primary outcome definition and/or its analysis will also be reflected in a protocol amendment. Any deviation from the original statistical plan must be described and justified in the final report. The statistical analysis will be conducted by means of SAS®.

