#### 8.3.1 Definition and analysis of primary outcome

The oxygenation of the patient is the primary outcome variable. The primary outcome will be assessed as the response rate of oxygenation to the intervention. As the patient's respiratory condition can vary over a broad range, may necessitate variable external support, and as these changes may occur over relatively short time periods, it is necessary to take all this into consideration when assessing oxygenation. Therefore we defined the parameters to be measured depending on the patient's condition to define a responder (Table 3.8-1). The majority of children included into the study are expected to be on supplemental oxygen or in room air. In these subjects oxygen saturation in room air will be assessed (for assessments please see 3.2). However to include the broad continuum of respiratory support possible in individual patients, an approach was chosen accommodating that need. Responses to treatment judged as significant were defined depending on Patient's condition. How and when to assess the variables is further detailed in the study protocol.

Oxygenation, the primary outcome parameter, was chosen as a dichotomous variable (response yes or no). Its components, i.e. O2-saturation and respiratory rate, are also used continuously in a descriptive manner as secondary outcome variables.

Tab 3.8-1: Definition of responders to treatment depending on Patient's condition

Patient's condition	Measured parameters	Specific metric	Definition of significant change or responder to the initiation of HCQ	Definition of significant change or responder to the withdrawal of HCQ	Method of aggregation
In room air	In room air O2 Sat (mean value) Respir rate (mean value)	Change from baseline	Increase $\geq 5\%$ in O2 Sat, or Decrease in resp. rate $\geq 20\%$	Decrease $\geq 5\%$ in O2 Sat, or Increase in resp. rate $\geq 20\%$	Proportion of responders
On O2-supplement	In room air O2 Sat (mean value) Respir rate (mean value)	Change from baseline	Increase $\geq 5\%$ in O2 Sat or Decrease in resp. rate $\geq 20\%$ or Support no more needed	Decrease $\geq 5\%$ in O2 Sat, or Increase in resp. rate $\geq 20\%$ or Support newly needed	Proportion of responders
On high-flow nasal cannula	O2-flow, air-flow	Change from baseline	Decrease $\geq 20\%$ or Support no more needed	Increase $\geq 20\%$ or Support newly needed	Proportion of responders

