2.1 Definitions

All subjects with signed informed consent are considered as **enrolled subjects**, even if they did not receive any trial treatment.

All randomised subjects will be included in the **Intention-to-treat (ITT)** populations. This population is the primary analysis population. Within ITT population analyses subjects will be assigned to the treatment to which they were randomised. For the combined analysis the ITT Population consists of all patients that are at least in the START or the STOP block.

The **safety** population comprises all subjects who received at least one dose of trial treatment. In analyses of the safety population subjects will be assigned to the treatment which they actually received.

The analysis populations will be defined prior to unblinding of the study.

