6.6 Primary Analysis

The variable assessing the primary outcome is the response rate measured by the oxygen saturation in room air.

START HCQ block

Relative change from trial day 1 (Visit 2) to day 28 (Visit 3) and day 56 (Visit 4) and from day 28 to day 56 change from active compound compared to change from placebo

STOP HCQ block

Relative change from trial day 1, i.e. Visit 2, through day 84, i.e. Visit 5: change from active compound compared to change from placebo

Both blocks separately

a) A difference between the changes in placebo and active phases is considered significant as described in the table below.

Patient's condition	Measured parameter	Definition of significant change or responder
Stable in room air or on	SpO2 in room air	Increase $\geq 5\%$

O2-supplement		
On high-flow nasal cannula	O2-flow, air-flow	Decrease $\geq 20\%$ or support not needed any more
Ventilated	Oxygenation index	Decrease $\geq 20\%$ or support not needed any more
On ECMO		Decrease $\geq 20\%$ or support not needed any more

The analysis will be done first by discarding the information on the patient's condition. Descriptive analyses will be done overall and for all patients conditions separately.

b) Patients are defined as responder as described in the table above. The numbers of responders are counted and compared by Fisher's exact test as well as logistic regression models with factors for treatment group and age group.

The following SAS code can be used:

```
PROC LOGISTIC DATA=indata;
  CLASS treatment age_gr;
  MODEL responder_YN = treatment age_group treatment*age_group;
RUN;
```

Both blocks together

Not applicable. There were too few patients in both blocks.

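### In STOP, the day-1-to-day-84 analysis has no rule for rescue or withdrawal for worsening, so a child who worsens and is treated back to baseline counts as stable

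*SAP*

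**What the plan says.** The STOP primary comparison in SAP 6.6 is "Relative change from trial day 1, i.e. Visit 2, through day 84, i.e. Visit 5: change from active compound compared to change from placebo". Protocol 3.3 and 8.3.1 define the same contrast. Room-air saturation is also measured at days 28 and 56, but those values do not enter.

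Protocol 4.2 foresees worsening: "It is possible, that some patients will deteriorate during the trial". It names no rescue drug and says that "it is in the responsibility of the treating physician to decide, what the further treatment will be". Protocol 4.1.10 bars pulsed glucocorticoids up to Visit 6 in STOP; a continuous oral dose is allowed "and has to be stable in the 4 weeks before entry into the study (day 1) and throughout the trail". Protocol 3.6.3 lists reasons for which a child may be withdrawn and leaves the choice open: "The investigator decides about withdrawal of subjects from the clinical trial in case of occurrence of criteria mentioned above". It also asks that a withdrawn child have the final-day examinations as far as possible.

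On analysis, SAP 2.1 states: "Within ITT population analyses subjects will be assigned to the treatment to which they were randomised". SAP 2.3 drops the per-protocol analysis and SAP 5.1 plans no substitution of missing values. Cumulative steroid equivalents are a separate secondary variable in SAP 6.7.1.

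The two documents define a STOP responder differently. The withdrawal column of protocol Table 3.8-1 counts worsening; for a child in room air this is a fall of at least 5% "in O2 Sat, or Increase in resp. rate" of at least 20%. The table in SAP 6.6 counts only improvement and has no withdrawal direction.

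**The concern.** STOP withdraws HCQ from stable children to see whether they get worse. Worsening is therefore the event of interest, and the physician's response to it can remove it from the data. If treatment succeeds, the child is back at the day-1 value on day 84 and looks like a child who never worsened. If the child leaves the trial and has no day-84 value, the child leaves the comparison.

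The rules in 4.1.10 and 3.6.3 govern conduct. Neither says how such a child is analysed, and without a per-protocol analysis a breach of the steroid rule does not alter the primary result. If worsening is more frequent on placebo, both routes move the result toward no difference, which would favour the view that HCQ can be stopped without loss. Steroid use would be visible in its own table, but it would not change how the child is classed in the primary outcome.

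**Working it through.** **No plan figure to reproduce.** Protocol 8.1 gives no formal sample size calculation. The documents state no worsening rate, rescue rate or alpha.

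**Step 1: what the written rules do to each child in STOP.**

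| Course of the child | Protocol Table 3.8-1 | SAP 6.6 table | Relative change |
|---|---|---|---|
| Never worsens | stable | non-responder | 0 |
| Worsens, not rescued | worsened | non-responder | negative (saturation) |
| Worsens, rescued to baseline by day 84 | stable | non-responder | 0 |
| Withdrawn for worsening, no day-84 value | left out | left out | left out |

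Rows 1 and 3 are the same in every column. Under the SAP table, row 2 is also a non-responder, so the loss in responder counts arises only under Table 3.8-1. The loss in relative change arises under either definition.

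**Step 2: inputs for an illustration.**
- Arm size: 80 subjects (protocol 8.1), an equal split between blocks (3.2) and 1:1 allocation (3.5.1) give 80 / 2 / 2 = 20 per arm.
- Test: two-sided Fisher's exact test (SAP 6.6). An alpha of 0.05 is assumed.
- Worsening and restoration rates: assumed throughout.

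**Step 3: one fixed example.** Suppose 9/20 placebo and 2/20 HCQ children worsen: 45% − 10% = 35 points, p = 0.031. Let r placebo children be restored, giving (9 − r)/20, or lost without a day-84 value, giving (9 − r)/(20 − r).

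| r | Restored | Difference | p | Lost | Difference | p |
|---|---|---|---|---|---|---|
| 1 | 8/20 | 30.0 | 0.065 | 8/19 | 32.1 | 0.031 |
| 2 | 7/20 | 25.0 | 0.127 | 7/18 | 28.9 | 0.058 |
| 3 | 6/20 | 20.0 | 0.235 | 6/17 | 25.3 | 0.109 |

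Each restored child costs 1/20 = 5 points. A lost child costs less.

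**Step 4: power under assumed rates.** Observed rate = true rate × (1 − f), with the same share f of worsened children restored in both arms. For 45% vs 10% and f = 0.25: 0.45 × 0.75 = 33.75% and 0.10 × 0.75 = 7.5%. Exact enumeration of Fisher's test with 20 per arm:

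| True rates | f = 0 | f = 0.25 | f = 0.50 |
|---|---|---|---|
| 40% vs 10% | 49% | 33% | 17% |
| 45% vs 10% | 62% | 43% | 23% |
| 50% vs 10% | 74% | 53% | 30% |

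With f = 0 there is no effect.

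**Step 5: the cost of the remedy.** Suppose 10% of otherwise stable children in each arm (assumed) are treated for another cause and counted as worsened. The rates become 0.45 + 0.55 × 0.10 = 50.5% and 0.10 + 0.90 × 0.10 = 19.0%. The difference is 31.5 points and power falls from 62% to 45%.

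**The case against.** **The figures do not describe SAP 6.6 as written.** This stands. They use Table 3.8-1, while the SAP table counts only improvement, and section 8 of the protocol lets the SAP modify the plan. The same section adds, however, that "any major modifications of the primary outcome definition and/or its analysis will also be reflected in a protocol amendment", and the current protocol keeps Table 3.8-1. The consequence is that any rescue rule for STOP must first put the withdrawal direction into 6.6.

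**Steroid rescue is an inference.** A reader might conclude that 4.2 permits steroids for worsening. It does not mention them, and a pulse or dose increase would breach 4.1.10. The point rests only on worsening being foreseen, treatment being left to the physician and no analysis rule covering the result.

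**Withdrawn children need not lack a final value.** A reader might assume that every withdrawn child is lost. Protocol 3.6.3 asks for the final-day examinations as far as possible. The SAP does not say whether these replace Visit 5, so the gap is narrower but remains.

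**There is little time to worsen and recover.** Protocol 1.3 gives a half-life of 30 to 60 days. On that range 52% to 72% of the drug remains at day 28 and 27% to 52% at day 56. Worsening caused by withdrawal may come late, so restoration of a quarter or half may be too high. STOP also enrols stable children, so 40% to 50% worsening may be generous.

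**The trial is exploratory, and ignoring rescue is a legitimate choice.** Both statements are fair. But the SAP does not present this as a deliberate choice, and dilution of the difference does not depend on a formal test.

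**Conclusion.** The point holds for STOP. Under the written rules, a child rescued to baseline by day 84 is counted as stable, and a child withdrawn for worsening without a day-84 value is omitted. If worsening is more frequent on placebo, both reduce the apparent effect of HCQ. The size cannot be stated: it is zero if nobody is rescued or lost, and the fall in power from 62% to 43% or 23% depends on assumed rates and on Table 3.8-1.

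A reader might go further and infer that the STOP result will be biased by a material amount. The documents do not support that, since they give no rate for worsening or rescue. In START the point is smaller: a worsening child is already a non-responder unless rescue lifts saturation by 5% or, under Table 3.8-1, another improvement criterion is met, such as a 20% fall in respiratory rate.

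The rule should be set before unblinding. Confidence is medium.

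**What to change.** Change SAP 6.6 only, before unblinding. Proposed text:

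> For STOP the responder definition is the withdrawal column of protocol Table 3.8-1. A child who, between Visit 2 and Visit 5, starts or increases systemic glucocorticoids, restarts open-label HCQ or starts another immunosuppressant for worsening of the lung disease, or is withdrawn for worsening, is counted as having met the withdrawal criterion whatever the day-84 value. For other withdrawn children the final-visit examination (protocol 3.6.3) is used as the Visit 5 value if available. In START a child with such an event between Visit 2 and Visit 3 is a non-responder at day 28. The analysis by observed value alone is reported as a sensitivity analysis, and relative change is shown with and without values after rescue.

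Leave protocol 4.1.10 and 4.2 as they are. Permitting steroids there would relax a restriction on conduct and is not needed to settle the analysis.

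No new data are required. Concomitant medication, exacerbations with any change in treatment, and the reason for withdrawal are already recorded.

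The cost is that treatment for infection or another trigger unrelated to HCQ withdrawal may be counted as worsening in both arms and dilute the difference, as in Step 5 of the working. For that reason the rule covers only treatment recorded as given for worsening of the lung disease, and the observed-value analysis is kept beside it.

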Statistical analysis	START HCQ block and STOP HCQ block The variable assessing the primary outcome is the response rate measured by the oxygen saturation in room air. Both blocks separately a) A difference between the changes in placebo and active phases is considered significant, if the oxygen saturation increases by $\geq 5\%$ . b) Patients are defined as responder if the oxygen saturation is increased by 5% compared to baseline. The numbers of responders are counted and compared by Fisher exact test. Both blocks together c) oxygen saturation and the correspondent responder will be analysed by a linear mixed model (or logistic regression respectively). If indicated, a Bayesian approach will be employed. If appropriate, the analyses will be adjusted for the stratification factor of the randomization: age group.

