## 1.2 Trial rationale

### The impact

So far, there exist no controlled studies to evaluate the efficacy of the different treatment options in chILD. In practice beside steroids hydroxychloroquine and macrolide antibiotics are often used drugs for the treatment of chILD (Clement 2010).

Due to the rareness of the diseases only international studies can collect sufficient numbers of patients. Therefore we will use the European wide project on chILD, the chILD-EU project, to implement a randomized controlled study to evaluate the pharmacological treatment of chILD.

This international study will address all these issues and will help to create new knowledge for everyday care in this broad group of pediatric interstitial lung diseases.

With this study we aim to

- Evaluate the efficacy of hydroxychloroquine against placebo in chILD
- Evaluate the safety of mid-term use of hydroxychloroquine
- Be able to make a decision on the risk and benefit of the use of hydroxychloroquine
- Help standardizing the pharmacological treatment of chILD

Currently HCQ is used off-label in a wide range of clinical severity, ranging from respiratory insufficiency to minimal respiratory symptoms. So far it is not predictable which patients will respond to the treatment and which will not. Due to this fact and due to the rareness of the diseases the goal of this exploratory study is to include patients with different symptoms and a wide range of clinical severity to sample as much information about this topic as possible to improve the treatment of this group of patients. Therefore, the character of this study is explorative and not confirmative.

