### 8.1 Sample size

Due to the exploratory nature of the study there is no formal sample size calculation. The study aims to include 80 patients.

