### 8.3 Efficacy analyses

The primary population for the analyses of efficacy are the ITT Populations (randomised patients) for each block. For the combined analysis the ITT Population consists of all patients that are at least in the START or the STOP block. For all hypotheses two-sided exploratory p-values will be provided.

If appropriate, the analyses will be adjusted for the stratification factor of the randomization: age group. The final efficacy analysis will be described in the Statistical Analysis Plan (SAP).

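### SAP 6.6(a) calls a between-arm difference significant by a per-patient responder threshold, with no test, standard error or interval tied to it

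*SAP*

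**What the plan says.** SAP 6.6 lists two separate items for each block.

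- **Part (a):** "A difference between the changes in placebo and active phases is considered significant as described in the table below". The table's last column is headed "Definition of significant change or responder". For patients in room air or on supplemental oxygen the entry is a rise in SpO2 of at least 5%. For high-flow, ventilated and ECMO patients it is a fall of at least 20% or support no longer needed.
- **Part (b):** "Patients are defined as responder as described in the table above", followed by "The numbers of responders are counted and compared by Fisher's exact test", together with logistic regression on treatment and age group.

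The protocol synopsis, statistical analysis item a), has the same rule for SpO2 alone: a difference between the changes "in placebo and active phases is considered significant, if the oxygen saturation increases by" at least 5%.

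Protocol 8.3 adds, for efficacy in general: "For all hypotheses two-sided exploratory p-values will be provided". Neither document ties a p-value, test or interval to part (a).

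**The concern.** The table describes how far one patient must move to count as a responder. Part (a) applies it to a different quantity, the difference between two arms. Whether an arm difference exceeds chance depends on the spread of the changes and the number of patients, and neither enters the rule.

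Two things are at stake. A report that follows (a) to the letter could print the word significant, or withhold it, on the size of the difference alone. Parts (a) and (b) also stand side by side as the primary analysis and can point in opposite directions, and the plan does not say which then governs.

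Part (a) is also hard to carry out as written. It does not say whose saturation must rise or against what. SAP 6.6 first ignores the patient's condition, yet the rows of the table are on different scales, so no single difference in change is defined across them.

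**Working it through.** There is no stated sample size calculation, alpha or power to reproduce: "Due to the exploratory nature of the study there is no formal sample size calculation". The figures below only illustrate how a fixed threshold behaves.

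**Inputs from the documents.** 80 patients allocated and an equal split between blocks (Protocol 3.2), with 1:1 allocation (Protocol 3.5.1). That gives 80 / 2 / 2 = 20 per arm per block.

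**Assumptions.** SD of the change in SpO2 from 4 to 15 points; 5% read as 5 absolute points; part (a) read as requiring an observed active-minus-placebo difference in mean change of at least 5; normal approximation; two-sided 0.05 as the comparison test.

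**Formulas.** SE = SD × √(2/n). Chance of meeting the rule in favour of active with no true effect = 1 − Φ(5/SE). Difference that a two-sided 0.05 z-test would need = 1.96 × SE.

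Example at SD 10: SE = 10 × √(2/20) = 3.16; 5/3.16 = 1.58; 1 − Φ(1.58) = 5.7%; 1.96 × 3.16 = 6.20.

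| Assumed SD | SE (n = 20) | Rule met, no true effect | Difference needed at 0.05 |
|---|---|---|---|
| 4 | 1.26 | 0.004% | 2.48 |
| 5 | 1.58 | 0.08% | 3.10 |
| 8 | 2.53 | 2.4% | 4.96 |
| 10 | 3.16 | 5.7% | 6.20 |
| 15 | 4.74 | 14.6% | 9.30 |

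The fixed rule agrees with a 0.05 test only near SD 8. Below that it is stricter; above that it is looser. With 10 per arm, an assumed shortfall, the chance with no true effect is 1.3% at SD 5, 13.2% at SD 10 and 22.8% at SD 15.

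**True effect of exactly 5 points.** The chance of meeting the rule is 1 − Φ((5 − 5)/SE) = 1 − Φ(0) = 50%, whatever the SD or the number of patients.

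**Conflict between (a) and (b), invented data, 20 per arm.**

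1. Every active patient gains 4 points and every placebo patient loses 1. The mean difference is 4 − (−1) = 5, so (a) is met. No patient gains 5, so there are 0/20 against 0/20 responders and Fisher's p = 1.
2. Five active patients gain 8 points and nobody else changes. The mean difference is 5 × 8 / 20 = 2, so (a) is not met. Responders are 5/20 against 0/20. The probability of that table is C(20,5)/C(40,5) = 15,504/658,008 = 0.0236; doubled for the mirror table, Fisher's p = 0.047.

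**Part (b) for comparison.** At an assumed two-sided 0.05 with 20 per arm, Fisher's exact test rejects with no true effect in 0.2% to 2.5% of trials, for common response rates from 5% to 50%. Its error is bounded whatever the response rate. That of (a) is not.

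**The case against.** The strongest reply is that the word was never meant statistically. The table header pairs a significant change with a responder. Protocol 8.3.1 uses the word in the same sense for individual responses, and its responder table aggregates by proportion of responders. On that reading (a) supplies the threshold and (b) does the testing. This is plausible and largely stands. It does not settle the matter, because the sentence in both documents is about the difference between the changes under placebo and active, and neither document states the intended sense.

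Three further points stand and limit the concern.

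- A reader might infer that the primary analysis has no test. It has: Fisher's exact test and logistic regression in (b), on the response rate that both documents name as the primary variable. SAP 6.7.1 also plans a between-group comparison of absolute SpO2 change, although it names no model or interval.
- A reader might infer that (a) destroys the trial's error control. The trial claims no confirmatory control: "Therefore, the character of this study is explorative and not confirmative". No alpha is stated anywhere, so lack of a controlled error rate is not peculiar to (a).
- A reader might infer that the mention of phases contradicts a parallel-group design. That is a fair query for STOP, but START placebo patients switch to active drug after day 28, so both phases exist within those patients.

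**Conclusion.** The concern holds as a defect of wording with a real consequence. As written, SAP 6.6(a) and synopsis item a) attach the label significant to an arm difference through a per-patient cut-off, and the result can contradict (b).

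The size is illustrative only. It rests on assumed SDs, 20 per arm, a normal approximation, and 5% read as absolute points, although the primary change is described as relative. Under those assumptions the chance of meeting the rule with no true effect runs from 0.004% to 14.6%.

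The figures do not support saying that the rule makes false claims of benefit easy. At the lower SDs it is far stricter than an ordinary test and would more often withhold the label from a real effect. What they show is that the error rate is set by an unknown SD and the achieved sample size, not by the plan. In an exploratory trial the harm is a misleading label. The change is advisable but not critical.

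**What to change.** In SAP 6.6 and the synopsis, state that all thresholds in the table, both the 5% SpO2 row and the rows with 20% or support no longer needed, serve only to classify individual patients as responders for (b).

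Replace (a) with text such as:

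> For each block, the between-arm difference in change in room-air SpO2 (START: day 1 to day 28; STOP: day 1 to day 84) is estimated with a 95% confidence interval from a linear model adjusted for baseline SpO2 and age group, in patients with room-air SpO2 measured. The result is exploratory. Patients on high-flow, ventilation or ECMO contribute through the responder analysis in (b).

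State whether the change is in absolute points or relative to baseline. If absolute, the same model can serve the SpO2 comparison in SAP 6.7.1, which names none.

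The cost is one extra simple model and aligned wording in two documents, with no new data. The introduction to Protocol section 8 requires a protocol amendment for major modifications of the primary outcome or its analysis, so the sponsor should decide whether this counts as one.
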